8.1.3 Assessment of Adverse Events

Each AE will be assessed by the Principal Investigator with regard to seriousness, intensity, and causality.

8.1.3.1 *Seriousness*

An SAE is defined as any untoward medical occurrence that:

- Results in death.
- Is a life-threatening adverse drug/device experience (this means that the patient is at risk of death at the time of the event; it does not mean that the event hypothetically might have caused death if it were more severe).
- Requires inpatient hospitalization or prolongation of existing hospitalization.
- Results in persistent or significant disability or incapacity.
- Is a congenital anomaly or birth defect.
- Is an important medical event that may not be immediately life-threatening or result in death or hospitalization, but that may jeopardize the patient or require intervention to prevent one of the above outcomes.

ANY SAE (INCLUDING DEATH) DUE TO ANY CAUSE, WHICH OCCURS DURING THE COURSE OF THIS INVESTIGATION, WHETHER OR NOT RELATED TO THE INVESTIGATIONAL DRUG, MUST BE REPORTED WITHIN 24 HOURS BY FAX TO

[REDACTED].

Medical and scientific judgment should be exercised in deciding whether a case is serious. Therakos, Inc. and/or its delegate (**[REDACTED]**) will determine if an event requires expedited reporting.

8.1.3.2 Intensity

The intensity of each AE must be assessed by the Principal Investigator using one of the following categories and recorded in the eCRF:

- Mild: an AE that does not interfere with usual activities.
- Moderate: an AE that interferes with usual activities.
- Severe: an AE that prevents usual activities.

8.1.3.3 Causality

The Principal Investigator will assess the causality/relationship between the study treatment and the AE, and record that assessment in the eCRF. The most likely cause of an SAE (e.g., disease under treatment, concomitant disease, and concomitant medications) will be indicated on the eCRF with details of the cause.

The causal relationship of the AE to study drug will be described for:

- Probable: the AE meets one of these criteria.
 - Follows a reasonable temporal sequence from administration of the study drug.
 - Could not be reasonably explained by the patient's clinical state, environmental or toxic factors, or other therapies administered to the patient.
 - Disappears or decreases on cessation or reduction in dose of the study drug.
 - Follows a known pattern of response to the study drug.
 - Reappears or worsens on rechallenge.
- Possible: the AE meets one of these criteria
 - Follows a reasonable temporal sequence from administration of the study drug
 - Could be reasonably explained by the patient's clinical state, environmental or toxic factors, or other therapies administered to the patient
 - Follows a known pattern of response to the study drug
- Unlikely: the AE meets one of these criteria
 - Does not follow a reasonable temporal sequence from administration of the study drug.
 - Could be reasonably explained by the patient's clinical state, environmental or toxic factors, or other therapies administered to the patient.
 - Does not follow a known pattern of response to the study drug.
 - Does not reappear or worsen on rechallenge.
- Not related:
 - The AE does not meet the above criteria.
 - There is sufficient information that the etiology of the AE is not related to the study drug.

For SAEs, the Principal Investigator will assess whether the event is related to UVADEX, the ECP procedure, concomitant medication, an underlying condition, other (specify), or unknown. If the SAE is assessed as related to UVADEX, the likelihood of the relationship will be assessed by the Principal Investigator as Probable, Possible, or Unlikely.

8.1.4 Recording Adverse Events

Adverse events will only be recorded from ICF signing until Week 16. Following Week 16 there will be a passive chart review which will not include the collection of AEs. Any AEs occurring after the end of the study should be reported to the Sponsor by the Investigator if the Principal Investigator considers that there is a causal relationship with the study treatment.

All AEs (including AEs resulting from active standard of care medication and study device), regardless of the relationship to study drug, will be recorded in the eCRF. In addition, the technician performing the ECP procedure will observe and record any AEs that occur during the procedure. Treatment will be stopped if the patient cannot tolerate the procedure.

All AEs recorded in the eCRF should contain a brief description of the event, date of onset, date of resolution, intensity, treatment required, relationship to study drug(s) and/or device, action taken with the study drug and/or device, outcome, and whether the event is classified as serious.

After receipt of the initial report, [REDACTED] Safety will review the information and, if necessary, contact the Principal Investigator to obtain further information for assessment of the event. [REDACTED] Safety will be responsible for all information processing and reporting according to local legal requirements following ICH E6 guidelines. Where necessary, Principal Investigators will inform the authorities in their own countries.

8.1.6 Follow-up of Serious Adverse Events

All SAEs experienced by a patient, irrespective of the suspected causality, will be monitored until the event has resolved, until any abnormal laboratory values have returned to baseline or stabilized at a level acceptable to the Principal Investigator and Medical Monitor, until there is a satisfactory explanation for the changes observed, or until the patient is lost to follow-up or the event is unlikely to resolve.

The Data Safety Monitoring Board (DSMB) meets on a quarterly basis to review all the SAEs (unblinded), the most frequent AEs (blinded aggregate data), and laboratory data of interest, and will make recommendation to the study team regarding the safety aspect of the study. The safety review team consists of medical experts who are not involved in the study.

8.1.7 Protocol-Specified Serious Adverse Events

In order to minimize expedited reporting on non-informative SAEs, the following list of events do not need to be reported individually in an expedited manner, as they are anticipated due to disease progression and/or the use of concomitant therapies. These events include:

- Relapse of an underlying pre-transplant malignant condition, progression of aGvHD symptoms, pancytopenia, vomiting, diarrhea, GI bleeding, bloody stools, GI perforation, myelosuppression, leukopenia, AST elevation ALT elevation, elevated bilirubin, hepatotoxicity, thrombocytopenia, red cell aplasia, hypogammaglobulinemia, anorexia, nephrotoxicity, seizures, and anemia;
- Tuberculosis infection, tuberculosis reactivation, CMV infection, VZV infection, herpes simplex virus infection, CMV reactivation, VZV reactivation, herpes simplex virus reactivation, parasitic infections, bacterial central line infection, bacterial sepsis, fungal central line infection, and fungal sepsis.

8.1.8 Suspected Unexpected Serious Adverse Reactions

A SUSAR is defined as any untoward and unintended response to a study drug, which is not listed in the applicable product information, which is assessed by the sponsor and or study investigator as being unexpected and meets one of the following serious criteria: results in death, is life-threatening, requires hospitalization or prolongation of an existing hospitalization, results in persistent or significant disability or incapacity, or is a congenital anomaly or birth defect:

- If the SUSAR is fatal or life-threatening, regulatory authorities and ethics committees will be notified within 7 calendar days after the Sponsor learns of the event. Additional follow-up information (cause of death, autopsy report, and hospital report) should be reported within an additional 8 days (15 days total).
- If the SUSAR is not fatal or life-threatening but is otherwise serious (meets the other seriousness criteria in [Section 8.1.3.1](#)), regulatory authorities and ethics committees will be notified within 15 calendar days after the Sponsor learns of the event.

The Sponsor will notify the Principal Investigators of relevant information about SUSARs that could adversely affect the safety of patients in a timely fashion. Follow-up information may be submitted if necessary.

The Sponsor will also provide annual safety updates to the regulatory authorities and ethics committees responsible for the trial. These updates will include information on SUSARs and other relevant safety findings.

8.1.9 Pregnancy

The Sponsor has a responsibility to monitor the outcome of pregnancies where there has been maternal exposure to the investigational drug.

Pregnancy alone is not regarded as an AE unless there is a suspicion that the study drug(s) may have interfered with the effectiveness of a contraceptive medication.

Elective abortions without complications should not be handled as AEs unless they were therapeutic abortions (see below). Hospitalization for normal delivery of a healthy newborn should not be considered an SAE.

All pregnancies must be reported by the Principal Investigator to [REDACTED] Safety on the initial pregnancy report form within 30 days after becoming aware of the pregnancy. The Principal Investigator must follow up and document the course and the outcome of all pregnancies even if the patient was discontinued from the study or if the study has finished.

All outcomes of pregnancy must be reported by the Principal Investigator to [REDACTED] Safety on the pregnancy outcome report form within 30 days after he/she has gained knowledge of the normal delivery or elective abortion.

Any SAE that occurs during pregnancy must be recorded on the SAE report form (e.g., maternal serious complications, spontaneous or therapeutic abortion, ectopic pregnancy, stillbirth, neonatal death, congenital anomaly, birth defect) and reported within 24 hours in accordance with the procedure for reporting SAEs.

If a partner of a male study patient who has been exposed to study drug becomes pregnant, every effort should be made to monitor the pregnancy and outcome of pregnancy. A separate ICF will be provided for the partner before any data are collected regarding the pregnancy.

8.1.10 Medical Device Reporting

All device malfunctions during the 12-week study period should be reported to the Therakos, Inc. support hotline. The Mallinckrodt Critical Care Customer Care phone numbers are [contact] in the United States and [name] in Europe. The caller should identify his/her involvement in this clinical study.

Device malfunctions should also be recorded in the eCRF. Any AEs resulting from the malfunction will be recorded in the eCRF.

8.2 DATA SAFETY MONITORING BOARD

A DSMB will be in place to oversee the study. The DSMB will be an external committee composed of various specialists (also relevant to the pediatric bone marrow transplant population being studied). Details will be provided in the DSMB Charter.

The DSMB will be responsible for ongoing review of enrollment, safety, and, if requested by the DSMB, efficacy data. They will provide regular assessments on the safety and overall risk-to-benefit ratio of the study conduct, advise Therakos, Inc. of the need for any protocol modifications/amendments to minimize potential risk for patients, and make recommendations including stopping of enrollment and/or treatment, if needed.

A [REDACTED] Safety designee will be responsible for the timely coordination and delivery of the data to the DSMB on a regular basis.

9. STATISTICAL METHODS

9.1 PLANNED SAMPLE SIZE

A total of 48 patients with steroid-refractory grade B-D aGvHD will be enrolled and receive at least one ECP treatment. The trial is designed to test the null hypothesis that standard therapy has an overall response (CR+PR) rate of 10% versus the alternate hypothesis that ECP plus standard therapy has a CR+PR rate not equal to 10% (the expected rate $\geq 27\%$). The overall Type I error rate and power for this design are 5% and 90.4%, respectively.

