	
rate of 10% versus the alternate hypothesis that ECP plus standard therapy has a CR+PR rate not equal to 10% (the expected rate $\geq 27\%$). The overall Type I error rate and power for this design are 5% and 90.4%, respectively.
 
This single-arm trial will have 1 interim analysis and a final analysis. After the first 24 patients enrolled into the study have completed at least 4 weeks of ECP treatment, significance will be declared if the CR+PR 2-sided P value vs the stated alternative is < 0.005, corresponding to an observed CR+PR rate $> 48\%$. A final analysis will be performed after all 48 patients enrolled into the study have been treated for at least 4 weeks. In this final analysis, significance will be declared if the CR+PR 2-sided P value vs the stated null is < 0.049.

Statistical methods	
All baseline demographic and disease characteristics will be summarized. The primary endpoint of overall response (CR+PR) at Day 28 (Week 4) will be summarized by frequency tabulation and analyzed using exact Binomial test and confidence interval. Secondary endpoints of response at Week 8 (Day 56) and Week 12 (Day 84) will be analyzed in the same manner. Other endpoint data collected in the Treatment and Follow-up Period will be summarized appropriately.
 
All AE data will be fully listed by investigator terms and Medical Dictionary for Regulatory Activities (MedDRA) preferred term. Adverse event data will be summarized by system organ classification and preferred term. Vital signs and laboratory values will be summarized by visit and numbers of patients, with excursions outside the normal reference range summarized.
 
Patients who voluntarily cease to receive treatment early will not be replaced. Patients may be replaced if they are enrolled in the trial but are not treated. If a patient has received any ECP treatments and is administered a second-line therapy other than ECP, or discontinues study treatment, that patient will be considered a nonresponder and may not be replaced.

TABLE OF CONTENTS

SIGNATURE PAGE.....	3
SIGNATURE PAGE.....	4
PROTOCOL SYNOPSIS	5
TABLES IN TEXT	14
FIGURES IN TEXT.....	14
LIST OF ABBREVIATIONS AND DEFINITIONS OF TERMS.....	15
1. INTRODUCTION	17
1.1 Background.....	17
2. STUDY OBJECTIVES	21
2.1 Primary Objective	21
2.2 Secondary Objectives.....	21
3. OVERALL DESIGN AND PLAN OF THE STUDY	22
3.1 Overview	23
3.2 Endpoints.....	23
3.2.1 Primary Endpoint.....	23

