9.2 OVERVIEW OF STUDY DESIGN

This single-arm trial will have 1 planned interim analysis and a final analysis.

The primary endpoint is whether a patient achieves an overall response (defined as a complete response (CR) or partial response (PR)). The trial is designed to test the null hypothesis that standard therapy has an overall response (CR+PR) rate of 10% versus the alternate hypothesis that ECP plus standard therapy has a CR+PR rate not equal to 10% (the expected rate $\geq 27\%$). After the first 50% (24/48) of the patients have been treated for at least 4 weeks (or fewer if patients discontinued treatment), significance will be declared if the CR+PR 2-sided *P* value versus the stated alternative is < 0.005 , corresponding to an observed CR+PR rate $> 48\%$. Based on the primary endpoint analysis and review of the safety results available at the time of the interim analysis, consideration will be given, in the absence of safety concerns, to continue or stop the study for success or futility. Enrollment will not be placed on hold during the interim analysis. A final analysis will be performed after all 48 patients have been treated for at least 4 weeks. In this final analysis, significance will be declared if the CR+PR 2-sided *P* value versus the stated null is < 0.049 . The overall Type I error rate and power for this design are 5% and 90.4%, respectively.

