9.3.1 Analysis of Primary Endpoint

The primary endpoint is the proportion of patients who achieve an overall response (CR+PR) after 4 weeks (Day 28), or fewer treatments if they discontinued treatment, of ECP treatment. Patients must receive at least one treatment. Patients will be evaluated by the treating physician for the presence or absence of aGvHD manifestations of the skin, liver, and gut; source data will be collected for each patient and entered into the eCRF, and a scoring algorithm will be applied to calculate the grade of aGvHD using the modified IBMTR Severity Index. If a Patient is administered a second-line therapy other than ECP for the treatment of aGvHD, or discontinues study treatment, that Patient will be considered a nonresponder. The primary endpoint will be summarized by frequency tabulation and analyzed using exact Binomial test and confidence interval. The formal statistical analysis and evaluation of response is based on at least 4-weeks ECP treatment data only.

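### The stated 90.4% power is not that of the planned exact binomial test, which needs at least 10/48 responders and has about 87.2% power at a 27% response rate

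*Combined protocol and SAP*

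**What the plan says.** Section 9.1 (Planned Sample Size) sets the size: "A total of 48 patients with steroid-refractory grade B-D aGvHD will be enrolled and receive at least one ECP treatment". It tests a null response rate (CR+PR) of 10% against a two-sided alternative, with an expected rate of at least 27%, and adds: "The overall Type I error rate and power for this design are 5% and 90.4%, respectively". The same power sentence appears in section 9.2 and in the synopsis under Power and sample size.

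Section 9.3.1 names the test: "The primary endpoint will be summarized by frequency tabulation and analyzed using exact Binomial test and confidence interval". The synopsis says the same under Statistical methods.

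Section 9.2 sets the final criterion, a two-sided "value versus the stated null is < 0.049". It also plans one interim analysis at 24 patients. Success there needs a two-sided P below 0.005, which the section equates with an observed rate above 48%. Stopping for futility is allowed, but no numerical rule is given.

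The document does not say how the power was calculated, and it does not state how many responders count as success at the final analysis.

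**The concern.** The exact binomial test can only succeed at whole numbers of responders, so its power moves in steps as the cut-off changes. With 48 patients and a 10% null rate, a power of 90.4% at 27% falls between two steps. It therefore cannot describe the test the plan specifies.

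The power is presented as a property of the 48-patient design, and readers rely on it to judge whether 48 is enough. If it is too high, the risk of a false-negative trial at the planning rate is larger than stated. Because no cut-off is given, readers also cannot see what result the trial needs.

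**Working it through.** **Inputs.** N = 48, null rate 0.10 and lowest expected rate 0.27 (section 9.1); exact binomial test (section 9.3.1); final two-sided P < 0.049, and an interim at 24 patients with two-sided P < 0.005 or rate > 48% (section 9.2).

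**1. Where 90.4% probably comes from.** The uncorrected normal approximation is

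Power = Φ[(p1 − p0 − z·√(p0(1−p0)/n)) / √(p1(1−p1)/n)]

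Here √(0.10 × 0.90/48) = 0.04330 and √(0.27 × 0.73/48) = 0.06408.

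- α = 0.05: (0.17 − 1.960 × 0.04330)/0.06408 = 1.329, giving 90.8%.
- α = 0.049: (0.17 − 1.969 × 0.04330)/0.06408 = 1.323, giving 90.7%.

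This comes within 0.3 to 0.4 points of 90.4% but does not equal it. With a continuity correction the approximation gives 87.7% to 87.8%.

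**2. The exact cut-off at the final analysis.** For X ~ Binomial(48, 0.10), the minimum-likelihood P adds the lower-tail outcomes that are no more likely than the one observed. At 9/48 and 10/48 that is only X = 0, with probability 0.0064.

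| Responders | Upper tail | Two-sided P, doubled | Two-sided P, minimum likelihood | Exact 95% CI |
|---|---|---|---|---|
| 9/48 (18.8%) | 0.0463 | 0.0926 | 0.0463 + 0.0064 = 0.0527 | 8.9% to 32.6% |
| 10/48 (20.8%) | 0.0187 | 0.0375 | 0.0187 + 0.0064 = 0.0251 | 10.5% to 35.0% |

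At 9/48 neither P value is below 0.049 and the interval includes 10%. At 10/48 both P values are below 0.049 and the interval excludes 10%. Final success therefore needs at least 10/48 under either convention.

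**3. The interim boundary.** For X ~ Binomial(24, 0.10), the two-sided P at 7/24 is 0.0075 (minimum likelihood) or 0.0149 (doubled). At 8/24 it is 0.0017 or 0.0034. So P < 0.005 means at least 8/24, whereas a rate above 48% means at least 12/24. Both readings are carried forward.

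**4. Overall power, no futility stop.** With interim cut-off r1 and final cut-off r,

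Power = P(X1 ≥ r1) + Σ over k < r1 of P(X1 = k) · P(X2 ≥ r − k), where X1, X2 ~ Binomial(24, p)

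| True rate | r = 10, interim ≥ 8/24 | r = 10, interim ≥ 12/24 |
|---|---|---|
| 27% | 87.23% | 87.15% |
| 28% | 90.11% | 90.05% |
| 30% | 94.34% | 94.30% |

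The shortfall at 27% is 90.4 − 87.2 = 3.2 points, and Type II error is 100 − 87.2 = 12.8% against a stated 100 − 90.4 = 9.6%. Power reaches 90.4% at a true rate of about 28.1%.

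**5. No other exact cut-off gives 90.4%.** At 27%, a final cut-off of 9 gives 93.1%, but step 2 shows that 9/48 fails the plan's own criterion. A cut-off of 10 gives 87.2%.

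**6. Type I error.** With a final cut-off of 10, the upper-tail error is 1.9% under either interim reading. The 5% limit is met.

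**The case against.** The strongest reply is that 90.4% is not a slip of arithmetic. The plan names no method for the power calculation, and a standard large-sample formula nearly reproduces the figure. On that view, the planning method and the analysis method merely differ. This is probably how the number arose, and it should be acknowledged. It does not rescue the sentence, which gives the power of this design, and the design's test is exact.

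A second reply is that the power is not expressly tied to 27%, since the expected rate is at least 27%, and 90.4% is reached about one point higher. But 27% is the only alternative rate given, and it is the natural planning value.

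A third is materiality. The earlier ECP studies cited in section 1.1 report overall response of 66% and 76%, and improvement in 70% of patients with acute disease; at such rates power exceeds 99.9%. This stands as a limit on the importance of the point, although section 1.1 itself says most ECP studies were small and retrospective.

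A fourth is that section 9.3 defers full analysis details to a formal analysis plan. The power claim, however, is made three times in the protocol, and nothing in the available text corrects it.

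Finally, 87% assumes no futility stop, although section 9.2 allows one. This is right, and it makes 87% an upper bound. As an illustration with assumed thresholds and the 8/24 success boundary, stopping at 2/24 or fewer gives 86.5%, and at 3/24 or fewer gives 83.9%.

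**Conclusion.** The point holds. For the exact two-sided test as planned, power at a 27% response rate is about 87.2%, not 90.4%. The result rests on N = 48, a null rate of 10%, final P < 0.049, the single interim analysis of section 9.2 and no futility stop. It does not depend on the two-sided P convention or on which interim boundary is meant.

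The error lies in a stated design property. It does not affect the decision rule, the sample size or the Type I error limit, and it would not change the interpretation of a positive result. It should be corrected, but the gap is small and disappears just above 28%.

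**What to change.** Replace the power sentence in the synopsis and in sections 9.1 and 9.2 with wording such as:

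> Using the exact binomial test, success at the final analysis requires at least 10/48 responders (20.8%). At a true response rate of 27%, and with no stopping for futility, power is about 87%. The overall two-sided Type I error is at most 5%.

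The cost is a wording change in three places and a stated power about 3 points less favourable. N stays at 48, and the success thresholds and the Type I error limit are unchanged.

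If a numerical futility rule is adopted, the power should be recalculated with it. Two related inconsistencies are best reconciled in the same edit: the two readings of the interim boundary in section 9.2 (8/24 and 12/24), and section 3.4, which describes two interim analyses at 19 and 38 patients instead of one at 24.
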